#### 4.1.4 Other EHR-Derived Outcomes

*Cross-reference: UNC IRBIS Application section A.9.1 (identifiers).*

Other measures collected through the PCORnet CDM include:

- Demographic information (birth date, sex, race, and ethnicity)
- Patient height and weight
- Health care provider information
- Death information (death date and source)
- Health care visit information (visit dates, primary payer, facility type, and provider ID)
- Diagnosis and condition information (condition data and type, diagnosis dates, and associated ICD/CPT codes) for:
  - Mental health disorders, defined by ICD-10 codes (e.g., depression, anxiety, schizophrenia, bipolar disorder, suicide attempt/intent)

- Number and type of CNCP conditions per ICD-10 codes (e.g., back pain, neck pain, headache, arthritis, HIV)
- Alcohol/substance misuse or abuse as measured by ICD-10 codes.
- Overall comorbidity using the Charlson Comorbidity Index per ICD-10 codes
- Opioid prescription information including RxNorm CUI (drug prescribed), prescription dates, dose, units, frequency, route, quantity, refills, and supply days.

We will calculate time to discontinuation of opioids, where discontinuation will be measured based on our previous work, except that the discontinuation will be defined as the first day of a minimum 90-day period with no opioid prescriptions (see Section 5.2 for additional information about the definitions and analyses).

A Schedule of Assessments indicating the timing and source of efficacy, safety, and fidelity measures is presented in **Table 6**.

## 4.2 Safety Evaluations

See Section 8 for information about the study's safety evaluations and procedures.

## 4.3 Process Evaluation

*Cross-reference: UNC IRBIS Application section A.9.1 (identifiers).*

The research team will develop a set of intervention fidelity measures to assess the extent to which the intervention was implemented as planned. The research team will evaluate fidelity via: EHR documentation review with a random sample of notes, clinical data extraction, and patient self-report. The measures are described in **Table 5**.

*Table 5. Process Evaluation*

Evaluation	Measure	Data Source
SDM intervention fidelity	Extent to which patients read or viewed SDM materials	Patient self-report (T2 and T3 surveys)
	Number of visits to an SDM-trained provider during the intervention period	Extracted from EHR using intervention-specific templates  Visit status data entered into REDCap by the Research Coordinator
	Content covered during SDM intervention visits	Provider report via EHR encounter notes using intervention-specific templates
MI+CBT-CP intervention fidelity	Number of intervention sessions attended	CBT session attendance logs which will be entered as visit status data in REDCap by the Research Coordinator
	Content covered during sessions	Provider report via EHR encounter notes using intervention-specific templates
Opioid care guidelines (GCC) fidelity	Elements of GCC covered, e.g. the patient has had a UDT within the past 12 months, Prescription Drug Monitoring Program [PDMP] was checked	Provider report via EHR encounter notes

Integrated Health Services to Reduce Opioid Use While Managing Chronic Pain: The INSPIRE Trial  
 (IRB Number: 18-0703)  
 Study Protocol, v16, 03/30/2022

**Table 6. Schedule of Assessments**

Measurement	Screening (Month -12 to 0)	Enrollment/ Baseline Survey (Month 0)	Baseline Clinical Data Extraction (Month -3 to 0)	Intervention visits (Months 1-12)	Clinical Data Extraction (Months 6, 12, 18)	T2 follow-up survey (Month 6)	T3 follow-up survey (Month 12)	Qualitative research activities
Informed consent	•							•
Demographics		•	•					
Randomization		•						
Average daily opioid dose			•		•			
Charlson Comorbidity Index (ICD-9/10)			•					
Chronic noncancer pain conditions (ICD-9/10)			•					
Mental health disorders (ICD-9/10)			•					
Alcohol/substance use disorders (ICD-9/10)			•					
Body mass index (based on height and weight)			•					
Health insurance payer		•	•		•			
Opioid withdrawal or overdose medication prescriptions			•		•			
Study intervention intensity (based on number of intervention visits)					•			
PROMIS self-report scales: (Pain Interference, Physical functioning, Pain Intensity, Anxiety, Depression)		•				•	•	
Brief Pain Inventory (11 key items)		•				•	•	
Health literacy level		•						
Patient centered communication		•				•	•	•
Self-reported relative opioid use						•	•	
Intent to taper		•				•	•	•
Use of intervention content						•	•	•
Satisfaction with care		•				•	•	•
Adverse Events and death review and evaluation			•	•	•	•	•	
Fidelity review and evaluation				•		•	•	

Cross-reference: UNC IRBIS Application section A.9.1 (identifiers).

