## 2.8 Inclusion and Exclusion Criteria

*Cross-reference: UNC IRBIS Application: A.2.7 (age range), A.3.1 (inclusion and exclusion criteria), A.4.2*

To be eligible to participate in this study, an individual must meet all the following criteria:

- Aged 18 to 85 years
- History of CNCP
- Receiving high-dose COT for chronic non-cancer pain (CNCP) as evidenced by current or most recent prescription of an average daily morphine-equivalent dose (MED) of 20 mg or greater for CNCP. Specific opioid analgesics are noted in Section 3.
- Receiving care at a participating clinic from a participating provider, as evidenced by at least 1 in-person visit within the past 12 months

Participants must be using at least 20 mg daily MED to be eligible for the study. If MED data are not available via the institution's data warehouse, a proxy of 3 or more opioid prescriptions to treat chronic pain within the past 12 months may be used to identify these patients in the prescreening phase. However, we will confirm in the EHR that the actual dosage prescribed is at least 20 mg daily MED. Because patients will be taking various opioid medications, daily opioid dose will be standardized to daily MED using standard opioid conversion tables.

An individual who meets any of the following criteria will be excluded from participation in this study:

- Not meeting the above inclusion criteria
- Opioid use is for pain directly related to an active cancer diagnosis
- Opioid use is for maintenance treatment of an opioid use disorder (OUD)
- Suicide attempt within the past 3 years
- Active suicidal ideation
- Currently receiving CBT
- Non-English speaking
- Other reason at the discretion of the investigator

Self-report screening items that are not ascertained via medical record data are provided in the **Participant Screening and Consent Script** (see attached).

Two exclusion criteria pertain to past medical history: a) If the patient does not have a history of chronic non-cancer pain, they will be excluded; b) if the patient has a history of suicide attempt within the past 3 years, they will be excluded. There is no exclusion based on accidents or injury.

Patients may be excluded for a limited set of other reasons based on the investigator's discretion. It is difficult to anticipate the rare, often unique types of situations in which a patient may not be fit for the intervention and to develop specific exclusion criteria for each hypothetical instance.

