4.7 Study Flow Chart of Assessments and Evaluations

Measurement	Screening (Month -12 to 0)	Baseline Survey (Month 0)	Baseline CDM Extraction (Month -3 to 0)	Intervention visits (Months 1-12)	CDM Extraction (Months 6, 12, 18)	T2 survey (Month 06)	T3 survey (Month 12)
Informed consent	•						
Demographics	•					•	•
Health literacy level		•					
Randomization		•					
Average daily MED			•		•		
Medical encounters			•		•		
Charlson Comorbidity Index (ICD-9/10)			•		•		
Chronic noncancer pain conditions (ICD-9/10)			•		•		
Mental health diagnoses (ICD-9/10)			•		•		
Alcohol/substance use diagnoses (ICD-9/10)			•		•		
Body mass index (based on height and weight)			•		•		
Health insurance payer			•		•		
Opioid withdrawal medication prescriptions			•		•		
Administer study intervention				•			
EHR template note					•		
Adverse Event Case Report form (as indicated)				•			
Brief Pain Inventory		•				•	•
PROMIS self-report scales: (Pain Interference, Physical functioning, Pain Intensity, Anxiety, Depression)		•				•	•
Current psychotherapy		•				•	•
Self-reported opioid use and intent to taper		•				•	•
Use of intervention content; knowledge check						•	•
Hospitalization or ED visits related to opioid use (overdose or withdrawal) or suicide attempt			•		•	•	•
Death					•		
Adverse Event review and evaluation	•	•	•	•	•	•	•
Fidelity review and evaluation				•		•	•

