5.2 Per-Protocol Population

As in most pragmatic clinical trials, some participants may not adhere to the intervention they were randomized to receive, reducing fidelity to the intervention as designed and potentially changing the effectiveness of the intervention. The most likely form of nonadherence will be absence from group therapy sessions in the MI+CBT-CP arm or with patients in the SDM arm ceasing interaction with the assigned provider. The potential impact of this nonadherence is underestimating the magnitude of the true treatment effect. To assess this, in addition to the ITT analyses, we will also conduct secondary analyses using a per protocol population consisting of participants that met all inclusion/exclusion criteria, and received a substantial portion of the randomized intervention, defined as at least 4 completed SDM visits and at least 4 completed MI or CBT sessions (out of a total of 1 MI and 8 CBT). Note that the inclusion criterion for baseline MED is based on the most recent prescription, while the baseline value for MED in the analysis is the average MED for the past 90 days. Having a baseline value < 20 is not a protocol violation when the sites indicated that inclusion criterion was met based on the most recent prescription when the patient was assessed. A sensitivity analysis on the per-protocol population will also be conducted by defining this population as those who met all inclusion/exclusion criteria and completed at least 3 SDM visits and at least 3 MI or CBT sessions. This sensitivity analyses are included as many SDM participants may only complete 3 visits with their provider throughout the 12-month intervention phase in the event their opioid prescriptions can be renewed over a 3-month period without an actual clinic visit.

The per-protocol analysis provides a better estimate of the true efficacy of an intervention (i.e., among those who completed the treatment as planned) (Ranganathan, Pramesh, & Aggarwal, 2016). No other analysis populations are defined for this protocol.

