Number of Unique Chronic non-cancer pain (CNCP) Diagnoses	Count	
A count of the total number of unique CNCP diagnoses from the EHR data (diagnosis codes were pulled 3-months prior to the randomization date); a list of all CNCP diagnosis codes can be found in the specifications file.
 
The ICD-10 codes used to classify the different CNCP ICD-10 codes was pulled from the Healthcare Cost and Utilization Project Agency for Healthcare Research and Quality (H-CUP-AHRQ) website (Clinical Classifications Software Refined (CCSR) for ICD-10-CM Diagnoses (ahq.gov))

Site	Categorical	3 different study sites – Duke, UNC, and Vanderbilt; Site is captured in the REDCap database
Number of Completed MI and CBT Sessions	Count and categories	
The total number of completed MI and CBT sessions will be derived from the REDCap database. Per the protocol, there is 1 MI session and 8 different group CBT sessions.
 
Categories will be defined as: Number of intervention sessions received: MI/CBT: 0, 1-2, 3-4, >4)

Variable	Type	Definition
Number of Completed SDM visits	Count and categories	
The participant's total number of SDM visits will be derived from the SDM sidecar request from each study site. Note: in the SDM sidecar dataset received from study sites, each documented SDM visit from a trained SDM clinician is supplied with the associated SDM visit date and delivery mode (in-person or telehealth). Only SDM visits within the 12-month intervention phase will be counted in the total number of completed SDM visits.
 
Categories will be defined as: Number of intervention sessions received: SDM: (0, 1-2, 3-4, >4)

Incidence of other types of pain treatments used	Binary and count	These are reported as collected on the T1-T3 survey (no derivations required) and include: non-opioid medications, over the counter pain reliever, topical pain relievers, herbal pain reliever, cortisone injections, acupuncture, hypnosis, meditation, yoga, massage, psychotherapy, CBT, chiropractic treatment, relaxation training, physical therapy, hydrotherapy, ice or heat therapy, Transcutaneous Electrical Nerve Stimulation (TENS), and other.

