We will test the interaction of intervention and 2 pre-defined subgroups (having at least one comorbid mental health condition (excluding substance use disorders) and sex) at the $p=0.10$ significance level. Model based analyses to evaluate heterogeneity of intervention effects by the specific subgroups will use a model analogous to those described above for the primary analysis (section 9.3); however, a subgroup type and the interaction between subgroup type and intervention arm will be added to the model. This addition will allow the study team to estimate difference between intervention for each subgroup category separately, and determine if there is a substantial difference in opioid change at 12 months between the subgroups for the SDM and MI+CBT intervention arms (interaction: does one intervention have substantially better or worse outcome than the other intervention for one of the subgroups but not the other subgroup). The general structure of the SAS code is shown below (example is for sex).

```

proc mixed data = INSPIRE_Primanaly method=REML;
  class Unique_ID intervention timepointN Sex clinic;
  model change_OpioidDose_MED = Intervention timepointN clinic
  base opioid intervention*timepointN Sex intervention*Sex
  intervention*Sex*timepointN / s residual DDFM=KR;
  repeated timepointN / type=toep group=intervention
  subject=Unique_ID R RCORR;
  lsmeans Intervention*Sex*timepointN / diff pdiff CL;
  lsmeans intervention*Sex*timepointN "CBT vs. SDM for Females at
  12-months"
    0 0 0 1 0 0 0 0 0 0 0 0
    0 0 0 -1 0 0 0 0 0 0 0 0/ CL;
  lsmeans intervention*Sex*timepointN "CBT vs. SDM for males at
  12-months"
    0 0 0 0 0 0 0 0 0 1 0 0
    0 0 0 0 0 0 0 0 -1 0 0 0/ CL;

  contrast "trt by sex interaction at 12m"
    Intervention*Sex 1 -1 -1 1
    intervention*Sex*timepointN
      0 0 0 1 0 0 0 0 0 -1 0 0
      0 0 0 -1 0 0 0 0 0 1 0 0/ CL;
run;
NOTE: Variable names may differ in the actual data.

```

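### The scheduled diagnosis extraction reaches back only 3 months and no look-back is fixed for the mental-health, substance-use and Charlson flags, so the baseline subgroups may be under-ascertained or filled in with post-randomisation codes

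*Protocol*

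**What the plan says.** **Schedules.** Protocol Table 6 has a column headed "Baseline Clinical Data Extraction (Month -3 to 0". The row "Mental health disorders (ICD-9/10" and the rows for substance use, Charlson and chronic non-cancer pain (CNCP) are marked in that column and in no other. SAP 4.7 keeps the window, as "Baseline CDM Extraction (Month -3 to 0", but marks "Mental health diagnoses (ICD-9/10" and the other three diagnosis rows a second time, in the extraction for months 6, 12 and 18. The screening column in both schedules spans Month -12 to 0 but carries no diagnosis extraction.

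**Definitions (SAP 9.2).** For the CNCP count, the "diagnosis codes were pulled 3-months prior to the randomization date". The mental-health and substance-use flags are set by any relevant diagnosis recorded in the EHR, and Charlson is a count of diseases. None of these three has a start or end date.

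**Entry (Protocol 2.8).** Being under care at a participating clinic is established "as evidenced by at least 1 in-person visit within the past 12 months".

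**Use.** SAP 9.6.4 tests interaction with arm at the 0.10 level for two subgroups: sex and "having at least one comorbid mental health condition (excluding substance use disorders"). SAP 9.6.5 adds ten exploratory covariates, including substance-use disorder and Charlson none versus one or more. Protocol 5.3.3 and SAP 3.1.3 intend the substance-use characteristic to cover past as well as current abuse.

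**The concern.** The entry criterion assures one in-person visit in a year, while the schedules extract diagnoses from one quarter of that year. A long-standing condition reaches the data only if someone coded it in that quarter, and a pain visit need not carry a code for depression, renal disease or an old substance-use disorder. A 3-month window is a poor fit for a characteristic meant to include past abuse.

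Two things could follow, depending on how the unstated look-back is resolved. If the flags rest on Month -3 to 0, true cases enter the flag-negative group, and the two subgroup-specific effects are pulled together. If codes from months 6, 12 and 18 are allowed to fill the gap, membership of a nominally baseline subgroup depends on health-care contact after randomisation. One arm is treated by psychologists, social workers or counselors (Protocol 6.3.1), so coding could differ by arm. Comparisons within subgroup would then no longer be between randomised groups, and the direction of the bias could not be predicted.

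**Working it through.** **1. Which codes can the flags see?**

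| Source | Mental-health, substance-use, Charlson | CNCP count |
|---|---|---|
| Protocol Table 6 | Month -3 to 0 only | Month -3 to 0 only |
| SAP 4.7 | Month -3 to 0, and months 6, 12, 18 | same |
| SAP 9.2 | no window stated | 3 months before randomisation |

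Neither schedule provides for a pre-randomisation code older than 3 months. The sources disagree on whether later codes are collected for these variables, and SAP 9.2 does not say whether they count.

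**2. Effect of missed cases if only Month -3 to 0 is used.** Let p be true prevalence and s the share of true cases coded in the window. Assume no false positives, and the same treatment effect in missed and captured cases. Let D1 and D0 be the arm differences in true cases and non-cases.

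- Flag-positive group: all true cases, effect D1.
- Flag-negative group: a share w = (1-p)/(1-ps) are true non-cases and the rest are missed cases, so the effect is w·D0 + (1-w)·D1.
- Observed interaction: D1 - [w·D0 + (1-w)·D1] = w·(D1 - D0).

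The interaction is therefore multiplied by w. Neither p nor s is in the documents. Illustrative values:

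- p=0.4, s=0.8: 0.6/0.68 = 0.88
- p=0.5, s=0.6: 0.5/0.7 = 0.71 (29% of the flag-negative group are true cases)
- p=0.6, s=0.5: 0.4/0.7 = 0.57

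Over a wider range, p 0.3 to 0.7 and s 0.5 to 0.9, w runs from 0.96 (p=0.3, s=0.9) down to 0.46 (p=0.7, s=0.5).

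**3. Power of the interaction test.** The plan states none for subgroups (Protocol 5.4), so I first checked the primary inputs. With a 10 MED difference, SD 40, two-sided 0.05 and 80% power, the normal formula gives 252 per arm and the t-test 252.1, rounded up to 253, the plan's figure. Power at 253 per arm is 80.3%. With 526 randomised and the plan's 20% inflation removed, 526/1.2 = 438 are evaluable and power is 74.4%, against 75% in SAP Table 6.1. The inputs reproduce.

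For the interaction, let q = ps be the flagged share. The standard error is 40·√[(4/N)(1/q + 1/(1-q))], tested two-sided at 0.10. With N=438 and p=0.5:

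| Capture s | Factor w | Power, true interaction 20 MED | Power, true interaction 10 MED |
|---|---|---|---|
| 1.0 | 1.00 | 83.5% | 37.0% |
| 0.9 | 0.91 | 76.5% | 32.5% |
| 0.7 | 0.77 | 60.9% | 25.1% |
| 0.5 | 0.67 | 44.8% | 19.5% |

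The interaction sizes are also assumptions.

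**4. Reach.** The primary model (SAP 9.3) contains arm, time, site, baseline dose and arm-by-time. The key secondary models are analogous. Neither contains a diagnosis flag. The CNCP count, the one diagnosis variable with a written 3-month window, is in neither the pre-specified nor the exploratory heterogeneity analyses.

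**The case against.** A reader might infer that the plan classes everyone without a code in that quarter as free of the condition, and that the mental-health test is therefore attenuated by 12% to 43%. The documents do not support that as a statement of fact.

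- SAP 9.2 puts no window on the mental-health, substance-use or Charlson variables, although it does write one for BMI, baseline dose and the CNCP count. SAP 4.7 collects these diagnoses again after randomisation. SAP 9.2 also refers to a dataset specification file, not available here, that may fix the look-back.
- It is tempting to cite SAP 5.2, where "their opioid prescriptions can be renewed over a 3-month period without an actual clinic visit", as proof that some participants have no encounter in the baseline quarter. That sentence explains low SDM visit counts in the intervention phase. It does not describe contact before randomisation. Telehealth contacts and recruitment at a clinic visit (Protocol 3.3.5 and 3.3.6) would put an encounter near randomisation for some participants.
- Protocol 4.1.4 also collects condition data, which might recover some cases. SAP 9.2 does not say that the flags use them.
- The percentages rest wholly on assumed prevalence and capture. If missed cases are milder and respond differently, the factor changes.
- Protocol 5.3.3 calls the subgroup test hypothesis-generating, and SAP 9.6.5 interprets the exploratory p-values descriptively.

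These points stand, and they make the claim conditional and its impact limited. They do not remove the problem. A flag can use only extracted data, no earlier code is scheduled, and recovering cases from follow-up codes replaces one defect with another. Cutting the flags at randomisation without lengthening the look-back would leave the under-ascertainment in place.

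**Conclusion.** The point holds in conditional form. Read together, the schedules and definitions leave two routes: a baseline flag drawn from one quarter, or a flag completed with post-randomisation codes. Under the first, the mental-health interaction is attenuated by (1-p)/(1-ps), illustratively to between 0.57 and 0.88 of its true size. This assumes no false positives, equal treatment effects in missed and captured cases, and values of p and s that the documents do not supply. Under the second, the direction of bias is unknown. The substance-use and Charlson covariates and the corresponding baseline summaries share the problem.

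The primary and key secondary analyses are unaffected. The change is worth making because it is cheap and serves one of only two pre-specified subgroup tests, not because the trial's main conclusion depends on it.

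**What to change.** In Protocol Table 6, SAP 4.7 and SAP 9.2:

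- Set the look-back for the mental-health, substance-use, Charlson and CNCP variables to Month -12 to 0, ending at randomisation. This matches the entry visit criterion.
- State that codes dated after randomisation do not enter these baseline flags, even where they are extracted for other purposes.
- Keep 90 days for opioid dose.
- Report the flags and the mental-health interaction with the 3-month look-back as a sensitivity analysis.

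The window belongs in the protocol as well as the SAP, because Protocol 10.1 limits transfers to protocol-specified elements. Twelve months will still miss older history, so the report should describe the substance-use flag as recorded in the past year.

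Cost: one date parameter in the query package that the coordinating center already supplies, and a sentence in each place. If data have already been pulled, sites must rerun the extraction and answer queries; SAP 4.4.3 allows about 2 months from initial to clean data. No patient contact or new data source is needed.
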